## 2. STUDY DESIGN

### 2.1 General Study Design

This randomized, double-blind, placebo-controlled multicenter, multinational study will assess the efficacy and safety of CINRYZE with protocol-mandated DSA reduction treatment and sucrose-free IVIg for the treatment of acute AMR in kidney transplant recipients. Eligible study subjects will have had a kidney transplant with adequate function defined as having a pre-AMR baseline  $eGFR_{MDRD} \geq 20 \text{ mL/min/1.73m}^2$  if the qualifying AMR episode occurs  $\leq 21$  days after transplant or pre-AMR baseline  $eGFR_{MDRD} \geq 30 \text{ mL/min/1.73m}^2$  if the qualifying AMR episode occurs  $>21$  days after transplant. The pre-AMR baseline is the highest  $eGFR_{MDRD}$  value obtained following the kidney transplant and within 30 days prior to the qualifying AMR episode. If more than 1  $eGFR_{MDRD}$  value is available, a mean of the 2 highest values (at least 1 day apart and both prior to the AMR episode) will be used as the pre-AMR baseline value. If no  $eGFR_{MDRD}$  was obtained within 30 days prior to the qualifying AMR episode, it can be evaluated within a 60-day period.

The qualifying episode of biopsy-proven AMR will be defined by 2013 Banff criteria and will have evidence of circulating DSA. Once the qualifying AMR episode is diagnosed through a biopsy, subjects will enter a screening period for additional eligibility assessments at the investigative site. During this screening, the first  $eGFR_{MDRD}$  value obtained after the qualifying biopsy should be used for the screening visit period. Biopsy slides and images (including, but not limited to EM) will be sent to an independent, blinded pathology Endpoint Adjudication Committee (EAC) for confirmation of AMR. Subjects will be stratified across centers for (1) living vs deceased donor and (2) severity of acute AMR as defined by screening period  $eGFR_{MDRD}$  ( $\leq 15 \text{ mL/min/1.73m}^2$  for severe, or  $>15 \text{ mL/min/1.73m}^2$  for mild to moderate). CINRYZE or placebo treatment should be started as soon as possible and within 7 days after the biopsy procedure.

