## 2.5 Determination of Sample Size

A total of 112 subjects (56 CINRYZE, 56 Placebo) will be randomized in a 1:1 ratio into 2 treatment groups: CINRYZE or placebo. Sample size was calculated for the primary endpoint and the key secondary endpoint using nQuery Advisor 7.0.

The primary endpoint in the study is the proportion of subjects with new or worsening TG at 6 months after treatment initiation. A 43% absolute difference in TG at 6 months between treatment groups (3/7 in placebo and 0/7 in CINRYZE) was observed in a subset of subjects (14/18) in the completed randomized Phase 2 pilot study (0624-201). For this study, the assumed proportion of subjects with new or worsening TG at 6 months will be 50% in the placebo group and 10% in the CINRYZE group. A sample size of 60 subjects (30 in placebo and 30 in CINRYZE) would be needed to obtain at least 90% power to detect a significant treatment difference at an alpha level of 0.025 (1-sided test).

The key secondary endpoint in the study is the proportion of subjects with all-cause graft failure. Assuming the proportions of subjects with graft failure due to AMR are 64% and 25% for placebo and CINRYZE, respectively, and all-other-cause graft failure rate is 12% for both placebo and CINRYZE, then the proportions of subjects with all-cause graft failure are 68% and 34% for placebo and CINRYZE, respectively. A total of 100 subjects will provide 90% power to detect an absolute treatment difference of 34% at an alpha level of 0.025 (1-sided test) for all-cause graft failure. These assumptions are based on literature ([Haririan et al. 2009](#); [Sharif et al. 2014](#); [OPTN/STRT Annual Data Report 2012](#)). Considering a 10% drop-out rate during the study, 112 subjects will be randomized to the study. Under these assumptions, the expectation is that there will be approximately 34 all-cause graft failures on placebo and approximately 17 all-cause graft failures on CINRYZE, giving 51 events total. The trial will continue until 51 such events are accrued and adjudicated by the nephrology EAC unless stopped prematurely based on findings at an interim analysis or until the final subject enrolled has been followed for 4 years post initial treatment with investigational product.

Additional eligible subjects may be enrolled based on the interim data analysis of the first 30 subjects who complete the Month 6 TG assessment for the re-estimation of sample size.

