## 2.6 Multiplicity Adjustments for Type I Error Control

To control the overall Type I error, the primary and key secondary endpoint will be tested hierarchically with a fixed sequence approach. The study will continue to assess the key secondary endpoint only if the primary null hypothesis has been rejected. Thus, the significance of the key secondary endpoint is contingent, and no adjustment for multiple endpoints is needed.

The primary endpoint will have 2 analyses (1 interim and 1 final for the primary endpoint). The first interim analysis is for futility and sample size recalculation. The second interim analysis, which serves as the final analysis for the primary endpoint, is for the assessment of efficacy (new or worsening TG at 6 months). The alpha level of 0.0001 is to be spent at the first interim

analysis in developing the efficacy boundary of the second interim analysis of TG at 6 months. The overall significance level for the efficacy analysis of primary endpoint will be preserved at 0.025 (1-sided test) by using a significance level of 0.0249 for the second interim analyses. The difference between treatments will be evaluated by using the CHW weighted test statistic (Cui et al., 1999).

The key secondary endpoint will have 3 analyses (2 interim and 1 final), at approximately 50% (~26 events), 75% (~39 events) and 100% (~51 events) of the targeted all-cause graft failure. The Hwang-Shih-DeCani alpha spending function with phi = -4, which is similar to the boundaries from the O'Brien-Fleming method, will be used for the unequal spaced timing of analysis. Using this approach requires  $z \geq 2.75$  (or equivalently  $p \leq 0.0030$ ) to consider stopping the study for a positive treatment effect at the first interim analysis (~50% of events),  $z \geq 2.43$  (or equivalently  $p \leq 0.0075$ ) to consider stopping the study for a positive treatment effect at the second interim analysis (~75% of events), and  $z \geq 2.01$  (or equivalently  $p \leq 0.0221$ ) to claim efficacy at the final analysis (~100% of events), as shown in the table below. This approach maintains a fixed sample p-value close to 0.025 (1-sided test) at the final analysis and an overall significance level at 0.025.

Analysis	Proportion of Targeted Number of Events	Z Scale	p-value (1-sided)
Interim 3	50%	2.751	0.0030
Interim 4	75%	2.428	0.0075
Final	100%	2.012	0.0221

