The purpose of the first interim analysis is to allow early stopping of the study for futility, assessing safety of the treatment, and potentially adjusting the sample size. The trial may be stopped for futility at the interim analysis or the sample size of the study may be adjusted up to ensure enough power to detect the treatment effect (section 14). The first interim analysis is planned to be performed when 30 subjects complete (half of the pre-defined sample size for primary endpoint, 15 subjects for each treatment group) the Month 6 visit. A fraction of alpha (0.0001) will be spent at the first interim analysis and accounted for in the overall type I error rate. Even if the value of test-statistics exceeds the efficacy boundary, the trial will not be stopped for efficacy. NOTE: For simplicity, 30 subjects complete the Month 6 visit and balanced arms are assumed to demonstrate statistical analyses in this document.

The futility of the study at the first interim analysis will be determined by calculating the conditional power (CP) based on observed trend at interim.

If the CP is  $< CP_{min}$ , the study will be stopped for futility. If the CP is between  $CP_{min}$  and 60%, the sample size will be adjusted up to make CP equal to 60%. The  $CP_{min}$  is the pre-specified lower limit of conditional power and will be specified in the DMC SAP before the 1st interim analysis. The analysis based on the adjusted number of subjects will be used for the final analysis on primary endpoint (i.e. second interim analysis in the study). The study will continue with the original planned sample size if CP is 60% or above.

The CP at the first interim analysis, assuming that the data that will be observed after the first interim analysis will follow the same distribution as seen at interim and the CHW weighted test statistic  $Z_{CHW}$  (Cui et al., 1999) as the final test statistic for second interim analysis (also see definition below), will be determined by the following formulae:

$$CP = P\left(Z_2 > \frac{Z_{1-\alpha} - w_1 Z_1}{w_2}\right)$$

$$= 1 - \Phi \left( \frac{Z_{1-\alpha} - w_1 Z_1 - \frac{\Delta}{\sqrt{\frac{2\bar{P}(1-\bar{P})}{n_2}}}}{w_2} \right)$$

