In order to demonstrate the stability of the primary analysis method, sensitivity analyses will be performed at the point of final analysis of primary endpoint (i.e. second interim analysis for study) by using multiple imputation (MI) assuming missing at random (MAR) to assign missing endpoint and/or combined with Cochran–Mantel–Haenszel (CMH) test for treatment effect. The CMH model will assess the treatment effect controlling for (1) donor characteristic (living vs deceased), (2) baseline AMR severity (severe vs mild to moderate) and possibly (3) time to onset of qualifying AMR from current transplant (>100 days vs  $\leq$ 100 days) if degree of freedom allows. Sensitivity analyses defined below will be based on the FAS.

	Statistical Test	Logic to assign the missing TG assessment at 6 months
Primary analysis model	Fisher's Exact with CHW weighted test	If no TG assessment at 6 months, assign as failure.
Sensitivity analysis 4	Fisher's Exact with CHW weighted test	If no TG assessment at 6 months, perform MI.
Sensitivity analysis 5	CMH with CHW weighted test	If no TG assessment at 6 months, assign as failure.
Sensitivity analysis 6	CMH with CHW weighted test	If no TG assessment at 6 months, perform MI

For multiple imputation, a monotone missing pattern will be assumed and logistic regression model will be utilized. The imputation seed will be 83789524 and number of imputations will be set as 100. The logistic regression model may contain the following factors (descending order by importance) to impute the missing TG assessment at 6 months:

- (1) Treatment group (CINRYZE vs placebo);
- (2) AMR severity at baseline (severe vs mild/ moderate);
- (3) Donor characteristics (living donor vs deceased donor);
- (4) Normalized eGFR change ( $\Delta_{eGFR}$ ).  $\Delta_{eGFR} = \frac{eGFR_{baseline} - eGFR_{last}}{T}$ , where   
 $eGFR_{baseline}$  is the last eGFR results prior to the first dose of investigational product,  $eGFR_{last}$  is the last eGFR result before or at Month 6 or early discontinuation visit, and T = (last eGFR assessment date – Date of first dose + 1)/30.25;
- (5) Resolution of qualifying AMR (Resolved by 6 months /early discontinuation vs unresolved by 6 months/early discontinuation);

(6) AMR free time in months, which defines as (date of Month 6 or early discontinuation visit – Date of first dose +1 – number of days with AMR)/30.25

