The difference between treatments will be evaluated by a Fisher's Exact test. If the p-value from the test is  $\leq 0.0030$  at first interim analysis (~50% of events), or  $\leq 0.0075$  at the second interim analysis (~75% of events), or  $\leq 0.0221$  at the final analysis (~100% of events), it will be concluded that CINRYZE is efficacious based on the proportion of subjects with all-cause graft failure and the result will serve as confirmatory evidence of clinical benefit based on all enrolled subjects.

Sensitivity analyses will be done at final analysis by using multiple imputation (MI) assuming missing at random (MAR) to assign missing key secondary endpoint and/or by using Cochran–Mantel–Haenszel (CMH) test for treatment effect. The CMH model will assess the treatment effect with controlling for (1) donor characteristic (living vs deceased), (2) baseline AMR severity (severe vs mild to moderate), and possibility (3) time to onset of qualifying AMR from current transplant ( $>100$  days vs  $\leq 100$  days) if degree of freedom allows. All the sensitivity analyses defined below will be based on the FAS.

	Statistical Test	Logic to assign the missing assessments for graft failure at 4 years (i.e. discontinued prior to 4 years)
Key Secondary Analysis Model	Fisher's Exact	Assign failure for subjects who discontinued prior to 4 years.
Sensitivity analysis 1	Fisher's Exact	MI for subjects who discontinued prior to 4 years.
Sensitivity analysis 2	CMH	Assign failure for subjects who discontinued prior to 4 years.
Sensitivity analysis 3	CMH	MI for subjects who discontinued prior to 4 years.

For multiple imputation for the key secondary endpoint, a monotone missing pattern will be assumed. The prediction model will consider treatment group, , AMR severity baseline, donor characteristic as factors with available post-dose eGFR results incorporated. The imputation seed will be 83789524 and number of imputations will be set as 100.

For sensitivity analysis 1, multiple imputation will be used to impute the key secondary endpoint outcome for all subjects who discontinued prior to 4 years. The p-values from Fisher's Exact tests will be computed for each imputed dataset and transformed to  $\chi^2$ -distribution with  $df = 2$  using Fisher's transformation as:

$$\Psi^{(m)} = -2 \log(p^{(m)}) \sim \chi_2^2$$

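### The two-stage Fisher test planned for the primary endpoint has about 85% power with 60 subjects, not the stated 90% or more, and the randomisation strata enter only its sensitivity analyses

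*SAP*

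**What the plan says.** Randomisation: subjects "will be randomized in a 1:1 ratio into 2 treatment groups". SAP 2.1 adds the strata: "Subjects will be stratified across centers for (1) living vs deceased donor and (2) severity of acute AMR as defined by screening period" eGFR, with the cut at 15 mL/min/1.73m².

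Primary sample size (SAP 2.5): the assumed rates are "50% in the placebo group and 10% in the CINRYZE group". The power statement is "A sample size of 60 subjects (30 in placebo and 30 in CINRYZE) would be needed to obtain at least 90% power" at one-sided 0.025.

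Primary test (SAP 10.1): the first stage is "half of the pre-defined sample size for primary endpoint, 15 subjects for each treatment group", and the second stage is planned at the same size. Formulae 1 adds Z_1 and Z_2 with weights √(15/30) each. Z_i is a pooled-proportion Z only if all four cells of the stage's 2×2 table exceed 5. Otherwise Z_i = Φ⁻¹(1 − p_i), with p_i from Fisher's test. The table of models names the primary as "Fisher's Exact with CHW weighted test". SAP 2.6 keeps the overall level at 0.025 "by using a significance level of 0.0249 for the second interim analyses".

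Key secondary (SAP 10.2): "The difference between treatments will be evaluated by a Fisher's Exact test", with a final threshold of p ≤ 0.0221.

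Strata: CMH tests controlling for donor type and AMR severity are sensitivity analyses 5 and 6 for the primary endpoint, and 2 and 3 for the key secondary. Sensitivity analysis 5 enters p-values of the CMH general-association statistic in Formulae 1.

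**The concern.** The power statement and the test have to describe the same procedure. SAP 2.5 makes no mention of two stages, yet the test in SAP 10.1 turns two 30-subject tables into Fisher p-values before combining them. Fisher's p-value is discrete and conservative in tables of that size, and the conservatism applies in each stage. If real power is well below 90%, a drug with the assumed effect is more likely to miss the primary endpoint. The key secondary endpoint then goes untested, because it is reached only through the primary.

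A second, separate point is that the confirmatory tests do not use the factors on which randomisation was stratified. The SAP treats the same factors as prognostic in its imputation, Cox and MMRM models.

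**Working it through.** **Inputs.** Rates 50% and 10%; 15 per arm in each of two stages; equal weights; threshold one-sided 0.0249, so z = 1.962; the switch rule of SAP 10.1. I take Fisher's p-value as one-sided, as the sample code in SAP Appendix 1 does, and assume no sample size increase at the first interim.

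**1. The stated figure.** Enumerating all binomial outcomes for one Fisher test with 30 per arm at 0.025 gives 91.4%. The statement in SAP 2.5 therefore reproduces, but for a single-stage test.

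**2. Which branch applies.** At 50% v 10% with 15 per arm, the probability that all four cells exceed 5 is 0.0016 per stage. The planned test is Fisher in practice.

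**3. The planned test and alternatives**, by exact enumeration over both stages:

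| Z per stage, combined by Formulae 1 | Power | Type I error, null rates 10% to 50% |
|---|---|---|
| SAP rule (Fisher in practice) | 85.1% | 0.1% to 0.9% |
| Unstratified pooled Z | 95.1% | 2.4% to 2.6% |
| Unstratified Z, hypergeometric variance | 94.7% | 2.4% to 2.6% |

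**4. Why.** Suppose each stage shows 6/15 placebo and 2/15 CINRYZE events.
- Fisher per stage: p = [C(15,6)C(15,2) + C(15,7)C(15,1) + C(15,8)C(15,0)] / C(30,8) = (525,525 + 96,525 + 6,435) / 5,852,925 = 0.107, so Z = 1.241. Combined: √½ × (1.241 + 1.241) = 1.75, below 1.962.
- Pooled Z per stage: pooled rate 8/30 = 0.267; Z = 0.267 / √(0.267 × 0.733 × 2/15) = 1.651. Combined: 2.34, above 1.962.
- One Fisher test on the same 60 subjects, 12/30 v 4/30: p = Σ C(30,a)C(30,16−a)/C(60,16) over a = 12 to 16 = 0.0195, below 0.0249.

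Only the stage-wise Fisher version fails to reject.

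**5. What stratification adds.** The documents give neither stratum prevalence nor prognostic strength. I assumed 50% to 60% for one donor type, 10% to 30% severe, and a common odds ratio for both factors. Simulated power (60,000 trials each):

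| Odds ratio per factor | SAP rule | Pooled Z | Signed CMH by four strata | CMH minus pooled Z |
|---|---|---|---|---|
| 1 | 84.8% | 95.0% | 94.2% | −0.8 |
| 2 | 85.6% | 95.4% | 94.8% | −0.6 |
| 3 | 85.8% | 95.7% | 95.8% | +0.1 |
| 5 | 86.8% | 96.2% | 96.9% | +0.8 |
| 10 | 87.8% | 97.1% | 98.5% | +1.4 |

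An exact stratified test gives the same message: 83.8% v 84.7% for Fisher at odds ratio 1, and 89.3% v 87.7% at odds ratio 5 (5,000 trials). Type I error of the signed CMH version is about 2.0% to 2.6%. If strata are left unbalanced between arms within a stage, a pessimistic case, its power is 92.2% to 95.3%.

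**6. Sensitivity analysis 5.** The general-association p-value is two-sided, so a stage favouring placebo can also give a large positive Z. Used as written, it has about 84% to 90% power (odds ratio 1 to 5).

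**7. Key secondary.** With 50 per arm and 68% v 34%, Fisher has 91.5% at 0.025, which reproduces the stated 90%. At the final threshold of 0.0221, final look only, Fisher has 89.4% and a pooled Z 92.4%: a gap of 92.4 − 89.4 = 3.0 points.

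**The case against.** A reader might infer that leaving out the strata costs the trial about 9 points of power, since 85% for the planned test sits beside 94% for CMH. The documents do not support that: the SAP's own pooled Z formula, with no strata, closes the whole gap. A reader might also infer that the plan ignores the factors. It does not; they are in pre-specified CMH sensitivity analyses and in several models. Nor is the planned test invalid. It controls type I error, and an unstratified test after stratified randomisation is acceptable, usually slightly conservative.

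The strongest counter-argument is that widening the normal-approximation branch would be a smaller repair and would recover the power on its own. That is correct. The case for CMH over a pooled Z rests on agreement with the randomisation, not on power.

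It is also fair that more than one sentence must change, because the conditional power and sample size rules in SAP 10.1 are written with the unstratified Z. Finally, SAP section 17 records that the study was discontinued after the first interim, that key secondary analyses will not be done, and that the primary gets simple summaries. No second-stage combination will take place, and redefining Z_1 now would follow an unblinded look. This limits the practical effect. It does not make the stated power right for the test as planned.

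**Conclusion.** The concern holds in two separate parts. First, the planned stage-wise Fisher test has 85.1% power at the design rates, about 6 points below the 91.4% of the single-stage test that fits the plan's statement (91.4 − 85.1 = 6.3), and it spends at most 0.9% of an allowed 2.49%. This part rests only on the SAP's own inputs, a one-sided Fisher p-value and no sample size increase. Second, the confirmatory tests do not follow the stratified randomisation, and the CMH analysis that would do so is specified without direction in sensitivity analysis 5. The power effect of stratifying is small, about −1 to +1.5 points, and depends on assumed stratum prevalence and strength. For the key secondary the gap is about 3 points, and the main reason to change is consistency with the randomisation.

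**What to change.** In SAP 10.1, define Z_i for each stage as the signed CMH statistic over the four randomisation strata. With N subjects, n₁ on placebo, n₀ on CINRYZE and m events in a stratum, E = n₁m/N and V = n₁n₀m(N − m)/[N²(N − 1)]. Then Z_i = Σ(observed placebo events − E) / √ΣV. Enter Z_1 and Z_2 in Formulae 1, align the conditional power and sample size formulas with this statistic, and keep the Fisher version as a sensitivity analysis. Make sensitivity analysis 5 use the signed statistic too. If the Fisher version remains primary, restate the power for 60 subjects in SAP 2.5 and protocol 9.6 as about 85%. In SAP 10.2, use the same stratified test.

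The cost is SAP wording and matching formula changes, with no new data. The downside is that the test is asymptotic rather than exact, and that strata with one arm empty contribute nothing.

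Given the termination, the change now amounts to adding a signed stratified result beside Table 14.2.1.1a, labelled post hoc. The CMH tables 14.2.1.3 and 14.2.1.4 are currently marked as not produced.

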### 10.1 Primary Efficacy Endpoint(s) and Analysis

The primary efficacy endpoint is defined as the proportion of subjects with new or worsening TG at 6 months post-treatment as adjudicated by the pathology EAC based on 2013 Banff criteria (standard score). New or worsening TG at 6 months by the standard score is defined as an increase of 1 or more between qualifying biopsy and 6-month biopsy. Subjects who do not have the TG assessment at 6 months post-dose will be assigned as failures, i.e. having ‘new or worsening TG’.

The primary analysis specified below will be performed based on the FAS for the first and second interim analysis of this study. As a sensitivity analysis, the primary analysis will be also performed based on Per-protocol Analysis Set-1 in the second interim analysis of the study.

The primary endpoint will be presented as the proportion of subjects with new or worsening TG determined at 6 months, and their difference between treatments (  $\Delta_{Cinryze-Placebo}$  ) is defined as follows:

$$\Delta_{Cinryze-Placebo} = \Pi_{Cinryze} - \Pi_{Placebo}$$

where  $\Pi_{Cinryze}$  is the proportion of new or worsening TG at 6 months post treatment in the CINRYZE group and  $\Pi_{Placebo}$  is the proportion of new or worsening TG at 6 months post treatment in the placebo group.

The analysis will employ a type I error rate of 0.025 to test null hypothesis:

$$H_0 : \Pi_{Cinryze} - \Pi_{Placebo} \geq 0$$

Against the 1-sided alternative:

$$H_a : \Pi_{Cinryze} - \Pi_{Placebo} < 0$$

There will be two interim analyses to assess the primary endpoint.

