For sensitivity analysis 4, multiple imputation will be used to impute the primary endpoint for subjects without TG assessment at 6 months. The p-values from Fisher's Exact tests will be computed for each imputed dataset and transformed to  $\chi^2$ -distribution with degree of freedom (df) = 2 using Fisher's transformation ([Fisher, 1932](#)):

$$\Psi_i^{(m)} = -2 \log(p_i^{(m)}) \sim \chi_2^2 \quad (\text{Formulae 2})$$

where  $p_i^{(m)}$  is the p-value from Fisher's Exact test and  $\Psi_i^{(m)}$  is the transformed  $\chi^2$ -distribution for the  $i$ -th interim stage ( $i = 1, 2$ ) of the  $m$ -th ( $m = 1, 2, \dots, 100$ ) imputed dataset.

Then, Wilson-Helferty transformation ([Wilson & Helferty, 1931](#); [Goria, 1992](#)) will be used to transform the  $\chi^2$ -distribution to an asymptotic normal distribution with mean 0 and variance 1, as following:

$$Z_{WH,i}^{(m)} = \frac{\left(\frac{\Psi_i^{(m)}}{df}\right)^{1/3} - \left(1 - \frac{2}{9 \times df}\right)}{\left(\frac{2}{9 \times df}\right)^{1/2}} \quad (\text{Formulae 3})$$

where  $\Psi_i^{(m)}$  is the  $\chi^2$ -distributed statistic from the  $m$ -th imputed dataset,  $df$  is the number of degrees of freedom associated with  $\Psi_i^{(m)}$ , and  $Z_{WH,i}^{(m)}$  is the transformed value.

The transformed normal statistics  $Z_{WH,i}^{(m)}$  will be combined using multiple imputation analysis for the first interim stage and the second interim stage, respectively. Then the combined statistics  $Z_{WH,1}$  and  $Z_{WH,2}$  will be used to calculate the CHW weighted test statistic  $Z_{CHW}$  as:

$$Z_{CHW} = \sqrt{\frac{15}{30}} Z_{WH,1} + \sqrt{\frac{15}{30}} Z_{WH,2} \quad (\text{Formulae 4})$$

For sensitivity analysis 5, the same approach for handling missing data as for the primary analysis will be considered. CMH test will be performed to evaluate the treatment effect with controlling for baseline AMR severity and donor characteristic. The p-values from CMH general association statistics for the first and second interim stages will be used to yield the CHW weighted test statistic  $Z_{CHW}$  as formulae 1.

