For sensitivity analysis 6, multiple imputation will be used to impute the primary endpoint outcome for subjects without any post-dose TG assessment and those who discontinued prior to Month 6 but had TG assessment at time of discontinuation. CMH test will be performed to evaluate the treatment effect controlling for baseline AMR severity and donor characteristic. The CMH general association statistics will be computed for each imputed dataset and transformed to asymptotic normal using Wilson-Helferty transformation as formulae 3. The transformed normal statistics  $Z_{WH,i}^{(m)}$  will be combined using multiple imputation analysis for first interim stage and second interim stage, respectively. Then the combined statistics  $Z_{WH,1}$  and  $Z_{WH,2}$  will be used to calculate the CHW weighted test statistic  $Z_{CHW}$  as formulae 4.

Details of transformation and sample SAS code for multiple imputation and Wilson-Helferty transformation can be found in Appendix 1 Transformation of CMH Test statistics AND Fisher's Exact p-value for Multiple imputation.

Descriptive statistics for the primary efficacy outcome will be provided for the following subgroups: donor status at transplant, AMR severity at baseline, age, sex, and race.

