Data Fisher WH;
  set FishersExact(Where=(Label1="Right-sided Pr >= F"));
  /*transform fisher's p to chi-square with df=2*/
  fisher_chi=-2*log(nValue1);
  /*transform chi-square with df=2 to standard normal*/
  fisher_value_wh=((fisher_chi/2)**(1/3) - (1-2/(9*2)))/SQRT(2/(9*2));
  fisher_sterr_wh = 1.0;
run;

/*perform CMH test*/
proc freq data=datain mi;
  tables AMR*Donor*Treatment*Response / cmh;
  ods output CMH=CMH;
  by _imputation_;
run;

/*perform WH transformation of p-value from CMH to normal*/
Data CMH WH;
  set cmh(Where=(AltHypothesis="General Association"));
  cmh_value_wh=((VALUE/DF)**(1/3) - (1-2/(9*DF)))/SQRT(2/(9*DF));
  cmh_sterr_wh = 1.0;
run;

/*MI analysis to combine statistics from each imputed dataset, take
Fisher's for example. CMH is similar*/
PROC MIANALYZE DATA=Fisher_wh;
  ODS OUTPUT PARAMETERESTIMATES=mian_Fisher_wh;
  MODELEFFECTS Fisher value_wh;
  STDERR Fisher_sterr_wh;
RUN;
```

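### Sensitivity analyses 5 and 6 feed an unsigned CMH statistic into a one-sided CHW test, which loses power and ignores the direction of each stage

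*SAP*

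**What the plan says.** SAP section 10.1 sets the primary null hypothesis against a directional alternative, a lower rate of new or worsening TG on CINRYZE ("Against the 1-sided alternative"). Z_CHW is judged at 0.0249. Each stage has weight √(15/30). Where a stage statistic comes from a p-value, the only conversion given is Z_i = Φ⁻¹(1 − p_i).

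The CMH analyses belong to a set introduced with a stated purpose: "In order to demonstrate the stability of the primary analysis method, sensitivity analyses will be performed". For analysis 5 (CMH, missing counted as failure): "The p-values from CMH general association statistics for the first and second interim stages will be used to yield the CHW weighted test statistic". For analysis 6 (CMH with multiple imputation): "The CMH general association statistics will be computed for each imputed dataset and transformed to asymptotic normal using Wilson-Helferty transformation", after which the pooled values go into the CHW sum.

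The CMH code in Appendix 1 selects the general-association row and transforms its value with no sign. The Fisher code in the same appendix does select a tail ("Right-sided Pr >= F"). Key secondary sensitivity analysis 3 in section 10.2 transforms the same CMH statistic for a hypothesis that is also one-sided.

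**The concern.** With two arms and a binary outcome, the general-association statistic is the square of a signed Mantel-Haenszel Z, so it is equally large for benefit and for harm. Entered as written, a stage favouring placebo raises Z_CHW as much as a stage favouring CINRYZE. A true benefit is also scored on a two-sided scale and then held to a one-sided limit.

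These analyses exist to show that the primary result survives stratification and a different treatment of missing data. If analysis 5 or 6 fell short after a primary success, a reader would suspect the strata or the missing data, when the cause could simply be a two-sided statistic. Stages that contradict each other could be read as consistent support.

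**Working it through.** **Inputs.** From SAP section 2.5: 50% vs 10%, 30 per arm. From section 10.1: 15 per arm per stage, equal weights, one-sided 0.0249 (critical value 1.9617), strata of donor type by AMR severity. The SAP gives no stratum shares, so 40/40/10/10% is assumed. Except where stated, data are complete, there is no sample size increase and the futility stop is not applied.

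**The plan's own figure.** The SAP states 60 subjects for at least 90% power. The normal approximation needs 26 per arm, or 31 with continuity correction. At 30 per arm, power is 94.3% (normal) or 91.4% (exact one-sided Fisher). The claim is met. The SAP gives no power for analyses 5 and 6.

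**The three stage statistics.**
- Signed CMH: Z = Σ(a − E)/√ΣV over strata. Here a is the number of placebo events, and E and V are its hypergeometric mean and variance. The general-association statistic is Q = Z².
- Analysis 5: Φ⁻¹(1 − p), with p = 2[1 − Φ(|Z|)].
- Analysis 6: (Q^(1/3) − 7/9)/√(2/9), which is the transform with df = 1.

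**What each stage must show.** With equal stages, a signed Z of 1.9617/√2 = 1.39 in each is enough. In analysis 5 the converted value must reach 1.39, so the two-sided p must be at most 0.083, which is |Z| = 1.74.

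**Opposed stages.** Take Z₁ = +2.17 and Z₂ = −2.17.
- Signed: (2.17 − 2.17)/√2 = 0.
- Analysis 5: p = 0.030 in each stage, converted value 1.88, Z_CHW = 2 × 1.88/√2 = 2.66.
- Analysis 6: Q = 4.71, transform (1.676 − 0.778)/0.471 = 1.91, Z_CHW = 2.70.

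Both exceed 1.96.

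**Power by normal theory.** The drift per stage is 0.40/√(2 × 0.3 × 0.7/15) = 2.39. Signed power is Φ(√2 × 2.39 − 1.96) = 92%. The unsigned versions give 81%.

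**Simulated CMH** (400,000 two-stage trials per scenario):

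| Placebo vs CINRYZE | Signed CMH | Analysis 5 |
|---|---|---|
| 50% vs 10% | 92.2% | 79.7% |
| 50% vs 20% | 64.8% | 42.8% |
| 50% vs 50% | 2.5% | 2.4% |
| 10% vs 50% (harm) | about 0% | 79.7% |

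The analysis 6 transform without imputation gives 80.1% at 50% vs 10%. Equal strata or shares of 55/35/6/4% leave analysis 5 at 79.6–80.4% and the signed test at 92.2–92.6%. With 10% missing at random and 100 imputations, analysis 6 gives 76.1% against 89.7% signed (20,000 trials, with arm-specific posterior draws standing in for the SAP's logistic model).

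**Confirming the primary result.** The primary test uses the normal approximation if all cells exceed 5 and one-sided Fisher otherwise. It succeeds in 85.2% of trials at 50% vs 10% and 49.1% at 50% vs 20%. Given primary success, analysis 5 falls short in 8.2% and 19.1%. The signed CMH falls short in 0.6% and 1.7%.

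**Effect of the futility stop.** The stop uses "conditional power (CP) based on observed trend at interim". CP_min is not stated in the SAP, so 0.1% to 20% was assumed. With no effect, analysis 5 crosses in 1.1–1.2% of trials, and half of those have stage 2 favouring placebo. Under reversed rates, crossing falls from 80% to at most 0.06%.

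**Key secondary analysis 3.** With 68% vs 34%, 50 per arm, the 0.0221 limit and imputation omitted, the unsigned transform gives 87.3% and the signed statistic 92.0% (200,000 trials).

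**The case against.** The strongest reply is about weight. These analyses are supportive, the primary test and its alpha are untouched, and the arm proportions would show direction. Sections 17 and 20 leave both CMH tables out of the abbreviated report. All of that stands, and it limits the point to the plan as written and to reuse of its text or code.

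The SAP also sets no pass mark for analyses 5 and 6. Reading them against the primary limit is natural, but it is a reading.

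The comparator can be challenged too. The signed CMH (92%) is more powerful than the primary test (85%), so it sometimes crosses when the primary does not. Counting disagreement in both directions, analysis 5 and the signed version differ from the primary about equally at 50% vs 10% (8.5% and 8.0% of trials). At 50% vs 20% the signed version differs more (17.3% against 12.3%). Agreement counts alone therefore do not favour the fix. They arise because Fisher's conservatism happens to offset the two-sided scoring, which does not supply the missing sign.

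The 8% also depends on the strata. With a single stratum, analysis 5 crosses in 85% of trials and fails to confirm in only 1.1%. That is not the planned stratified analysis, and the gap to the signed version (94.6%) remains about 10 points.

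Finally, the text for analysis 5 does not say whether p is one- or two-sided, and the Appendix 1 code is only a sample. A programmer might add direction, but nothing tells them to. For analysis 6 the body text itself specifies the unsigned transform.

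**Conclusion.** The concern holds. As written, analyses 5 and 6 are two-sided within each stage and blind to direction, although they are read on a one-sided scale. The cost at the planned effect is about 12 to 14 percentage points of power against a signed CMH, assuming 15 per arm per stage and four strata. Within that, the result hardly depends on the shares tried. The share of primary successes left unconfirmed (8% at 50% vs 10%, 19% at 50% vs 20%) is more sensitive to the strata. Total null rejection stays near 2.5%, but part of it comes from stages favouring placebo. False support under true harm is a practical risk only if the futility stop is not applied. This is a stated rule that gives the wrong quantity, so it should be corrected, but it does not threaten the primary conclusion.

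**What to change.** In section 10.1, define the stage statistic for analyses 5 and 6 as Z_i = sign(stratum-adjusted risk difference, placebo minus CINRYZE) × √Q_CMH,i, or use the matching one-sided p-value. Then combine the stages with the existing CHW weights.

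The sign must be explicit. Halving the two-sided p without it gives |Z_i|. The sum (|Z₁| + |Z₂|)/√2 is the larger of |Z₁ + Z₂|/√2 and |Z₁ − Z₂|/√2, which are independent under the null, so it would cross with probability 1 − (1 − 2 × 0.0249)² = 9.7%.

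For analysis 6, pool the signed Z (standard error 1) or the Mantel-Haenszel risk difference across imputations by Rubin's rules. Put that in Appendix 1 in place of the Wilson-Hilferty step for the CMH chi-square. Use the same signed statistic in key secondary sensitivity analysis 3. Leave the Fisher branch as it is.

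The cost is a few lines of SAP text and SAS code, with no new data or subjects and no change to the primary analysis.
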